The design of the study is a randomised clinical trial (that will be registered at clinicaltrials.gov). Breast cancer patients will be randomised into two groups (group 1: intervention or group 2: control). The patients will be randomized using the Efron's biased coin design. (Efron, 1971) Patients are stratified by duration of radiation therapy/intervention (3 weeks vs. 5 weeks), type of surgery (mastectomy vs. breast conserving surgery and axillary lymph node dissection vs. sentinel node biopsy), and chemotherapy sequence (none vs. sequential vs. concomitant chemotherapy). Randomisation occurs when the informed consent is signed by the patient. Patients need to be referred as eligible candidates by an MD and can give consent only following an intake conversation, giving all information concerning the trial by going through the informed consent with the patient. This design is shown in figure 2.

[figure not shown]

Figure 2: Design of the study.

8) Medical device

Andullation® technology is a horizontal vibration technique, with stochastically modulated vibrations. Lievens (2007) described Andullation® as “a new vibration therapy introduced for medical application approved by the TÜV Rheinland Belgium N.V. and FDA massage mattress VM9100RM”. The technology is build-in in a massage mattress. Several studies show that vibration (Prisby et al., 2008) and horizontal position (Nepal et al., 2012) in general have a positive influence on relaxation, without side effects. References concerning the technology can be found at <http://www.iaat.eu/science/>

The medical device has a CE-mark in classification Pc IIa, type bf with certificate number Z-18-051-P and identification No. 0633.

Composition and dosing

Group 1 (intervention group): 3 to 5-week Andullation® intervention* (depending on and as long as the duration of the radiation therapy) will be performed, 3 times a week for 20 minutes. Patients wear comfortable clothing. The position of the medical device is adapted to the body contours of the patient for an ergonomic position. The patient is lying in a relaxed position with hands posed next to the body on the lateral side of the mattress.

* <https://www.hhp.be/nl/producten/andumedic-3-professional>

Medical device: Andumedic® 3 Professional

Settings of the medical device: a combination of program 3, 8 and 18 (standardized)

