Questionnaire		- Distress Thermometer	- Brief Pain Inventory (BPI) - Numeric Pain Rating Scale (NRS)		- Pittsburgh Sleep Quality Index (PSQI) - Insomnia Severity Index (ISI)	- EORTC QLQ BR23

Measurement moment	Before, during and after each intervention	Baseline After each 3 rd intervention Follow-up	NRS: Before and after each intervention, Follow-up BPI: baseline, after each 3 rd intervention and follow-up	Baseline After 3 weeks After 5 weeks (if radiation lasts 5 weeks) Follow-up	Baseline After 3 weeks After 5 weeks (if radiation lasts 5 weeks) Follow-up	Baseline After 3 weeks After 5 weeks (if radiation lasts 5 weeks) Follow-up
--------------------	--	--	--	--	--	--

Table 2: Procedures of the study.

[figure not shown]

Figure 1: These measurements will be repeated in week 3 and if your radiation therapy has a duration of more than 3 weeks, these measurements will also be repeated in week 5.

Questionnaires

- Distress Thermometer
A questionnaire to evaluate in what extent the patient experiences complaints like distress and anxiety, on a visual thermometer. (Mitchell et al., 2007)

- EORTC QLQ BR23
A questionnaire designed to investigate the quality of life in breast cancer patients. (Michels et al., 2013)
- Brief Pain Inventory
This questionnaire was designed to investigate the extent of pain and the influence of it on quality of life. (Abahussin et al., 2018)
- Pittsburgh Sleep Quality Index (PSQI)
This questionnaire was designed to assess sleep quality, quantity and disturbance. (Beck et al., 2004)
- Insomnia Severity Index (ISI)
This questionnaire was designed to assess the severity, nature and impact of insomnia over the past two to four weeks. (Morin et al., 2011)

Body parameters

- ANSWatch®
A device measuring heart rate through skin sensors. With the information withdrawn, the device calculates heart rate variability. (Sun et al., 2011)
- Perometer®
A device measuring arm contours with the use of infrared light. It is an efficient, safe, painless and reliable method to examine arm volumes. (Adriaenssens et al., 2013)
- Bioimpedance
By using bioimpedance, body composition will be estimated. Patients have to stand on scale and hold on to a handgrip that is connected with the scale. A small current will determine the body composition and especially extracellular fluid. This is a painless and innocuous examination. (Seward et al., 2016)

11) Flowchart

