Inclusion (and intervention) will start from the moment we receive a positive advice of the Medical Ethical Comité and will last for 14 months. The project (VUB Chair) is assigned for 24 months in total. An MD will refer patients as potential candidates for the trial after screening of the inclusion criteria and during the intervention, there will always be at least one MD in the PR4 building. (cfr table 1 and figure 2)

12) Randomisation/blinding:

The patients will be randomized using the Efron's biased coin design. (Efron, 1971) Patients are stratified by duration of radiation therapy (3 weeks vs. 5 weeks), type of surgery (mastectomy vs.

breast conserving surgery and axillary lymph node dissection vs. sentinel node biopsy), and chemotherapy sequence (none vs. sequential vs. concomitant chemotherapy).

Blinding is not possible.

13) Prior and concomitant therapy:

The patients are allowed to use every medication needed for their treatment before, during and after the intervention.

Any medication that has an influence on HRV activity, sleep, stress, edema and pain are reported before intake in the trial and monitored throughout the study.

14) Study analysis:

Sample size calculation

Based on our calculation in G*Power (with a medium effect size of 0.5 and with a power = 0.8), the total sample size is 128.

[figure not shown]

Figure 5: Sample size calculation

Analysis of the samples and statistical analysis

The promotor and researcher of the VUB Chair will analyze the samples and do the statistical analysis.

For all statistical analyses, superiority will be based on a two-sided p-value < .05. All statistical computations use SPSS v. 20.0 (IBM Corporation, Somers, NY, 10589, USA). Descriptive statistics will be used to describe medical and demographic characteristics of the population. Normality and homogeneity for both groups will be calculated. The repeated measures ANOVA design will be used to evaluate the changes over time and between groups. Correlations between outcome measures will be calculated as well.

15) Quality control and quality assurance:

The researcher will be present when the intervention is given to install the patient, to start the intervention and to make sure that everything runs according to plan.

The researcher will also make sure that all settings are properly programmed and placed as indicated in the protocol prior to welcoming the patient. The researcher will use the same checklist before starting each intervention.

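### The stated power of 0.8 at N=128 matches a single two-group comparison and is not established for the repeated measures ANOVA, the only between-group analysis written

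*Combined protocol and SAP*

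**What the plan says.** All of this is in the combined protocol and SAP.

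- **Section 14, on the number of patients:** "Based on our calculation in G*Power (with a medium effect size of 0.5 and with a power = 0.8), the total sample size is 128". The readable text names no test. The calculation is in Figure 5, which is not shown.
- **Section 14, statistical analysis, success criterion:** "For all statistical analyses, superiority will be based on a two-sided p-value < .05".
- **Section 14, statistical analysis, between-group method:** "The repeated measures ANOVA design will be used to evaluate the changes over time and between groups". The text does not say which ANOVA term decides superiority, how many time points enter, what within-patient correlation is assumed, or whether the pre-treatment value is a response or a covariate.
- **Section 10, Table 2:** the primary outcome, HRV, is measured "Before, during and after each intervention". Section 8 gives three sessions a week for 3 to 5 weeks. That is 9 to 15 sessions and, at three readings each, 27 to 45 HRV values per patient. Only the reading before the first session precedes all treatment.

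**The concern.** The figure of 0.8 appears to belong to one test and the success criterion to another. A repeated measures ANOVA on two arms gives two candidate tests of treatment, and neither is the two-group t-test.

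- **Between-groups F.** It compares each patient's average over every time point entered. If the pre-treatment value is one of them, a point with no treatment difference is averaged in and the contrast shrinks.
- **Group-by-time F.** It tests whether the arms' profiles differ. Its power depends on the within-patient correlation and on the number of time points, and the plan gives neither.

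A null result would be read against the printed 0.8. If the term actually used has much lower power, the trial could be taken for an adequately powered negative when it was not. The trial is also unblinded, and the promotor and researcher do the analysis themselves, so an open choice of deciding term is better closed in advance.

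**Working it through.** **Inputs from the plan:** effect size 0.5, power 0.8, total 128, two-sided .05 (section 14); two arms (section 7). **Assumed:** 1:1 allocation (64 per arm), all 128 evaluable, 0.5 read as d on the SD at a single time, compound symmetry with correlation ρ = 0.3, 0.5 or 0.7, one pre-treatment value with no difference, and k later values each with the full d=0.5. Write m = k+1.

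**1. Reproduce the plan's figure.** Two-sample t-test, noncentrality 0.5 × √(64/2) = 2.83 on 126 df: power 80.1%. With 63 per arm it is 79.5%, so 64 per arm (128 in total) is the smallest balanced size. A one-sided test would need 51 per arm (102).

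G*Power's repeated measures formulas (2 groups, ρ=0.5, 2 to 10 measurements) give these totals:

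| | f=0.5 | f=0.25 |
|---|---|---|
| between factor | 26 to 20 | 98 to 72 |
| interaction | 12 to 6 | 34 to 14 |

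None is 128.

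**2. Between-groups F.** Standardised effect e = 0.5(k/m) / √[(1+(m−1)ρ)/m], tested with 1 and 126 df. At ρ=0.5:
- k=1: 0.25/√0.75 = 0.289, power 37%
- k=2: 0.333/√0.667 = 0.408, power 63%
- k=3: 0.375/√0.625 = 0.474, power 76%

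Simulation (8,000 runs per case) gave 37% for k=1 and 75% for k=3 at ρ=0.5.

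**3. Group-by-time F.** λ = 32 × 0.25(k/m)/(1−ρ), with m−1 and 126(m−1) df. At ρ=0.5:
- m=2: λ = 8.0, power 80%
- m=27: λ = 8 × (26/27)/0.5 = 15.4 on 26 and 3,276 df, power 56%

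**4. Results at 128 evaluable patients (power in %, ρ = 0.3 / 0.5 / 0.7).**

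| Later values k | Between-groups F | Group-by-time F |
|---|---|---|
| 1 | 41 / 37 / 33 | 66 / 80 / 95 |
| 2 | 73 / 63 / 55 | 69 / 84 / 97 |
| 3 | 86 / 76 / 67 | 68 / 84 / 97 |
| 9 | 99 / 93 / 84 | 58 / 75 / 95 |
| 26 | 99.7 / 96 / 89 | 39 / 56 / 85 |

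If the effect builds linearly to 0.5 at the last value, the between-groups F has 53/43/36% with three later values and 64/47/38% with nine. With 45 values and a constant effect, the group-by-time F has 44% at ρ=0.5.

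**5. One value per patient.** At 128 and full effect:
- A single later value, unadjusted: 80.1% at any ρ.
- The mean of k later values, effect 0.5/√[(1+(k−1)ρ)/k]: 94/90/86% for k=2, and higher for k=9.
- A single later value adjusted for the pre-treatment value, effect 0.5/√(1−ρ²): 84/90/98%.

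A gradual effect costs this test too. With k=3, a linear build-up and ρ=0.5, the mean difference is 0.333. Unadjusted, 0.333/√0.667 = 0.408 gives 63%. Adjusted, 0.333/√(0.667−0.25) = 0.516 gives 83%. The between-groups F has 43% in the same case.

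**The case against.** The strongest reply is that nothing in the plan selects the unfavourable case.

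- **The 0.5 may be standardised on change.** Section 14 gives only "with a medium effect size of 0.5 and with a power = 0.8" and does not say which SD is meant. With two time points, the group-by-time F is the square of the t-test on change scores. If 0.5 is the standardised difference in change, 128 patients give 80.1% whatever the correlation. This stands, and it is a natural reading of an analysis aimed at changes over time.
- **The low figures need few time points.** No section restricts the HRV analysis to two values. Table 2 yields 27 to 45, and the Baseline entries there belong to the secondary outcomes. With 26 later values at full effect the between-groups F is above 80%. This stands for that term. It does not rescue the other one: at 27 values the group-by-time F falls to 39/56/85%.
- **The sized test is inferred.** Figure 5 might name another option. The repeated measures totals above were run at ρ=0.5 only. With f=0.25 and two measurements, the between-factor total rises to 122 at ρ=0.9 and 126 at 0.95. The t-test match is exact and likely, but not certain.
- **A mean over sessions is not literally what was sized either.** This is true, because its SD also depends on ρ. But at full effect its power is never below that of one later value, so the stated 0.8 holds for it as a floor at 128.

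A reader might infer that the trial is underpowered, or that a real medium effect is more likely to be missed than found. The documents do not support either. Both require the between-groups F to be the deciding term, the pre-treatment value to be a response in it, and few time points or a gradual effect. The plan states none of these.

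**Conclusion.** The concern holds as a mismatch between sizing and analysis: the printed 0.8 is not established for the planned test. It fits a two-group comparison of one value per patient (80.1%). Under the same effect, the two ANOVA terms range from about one third to above 99%, depending on choices the plan leaves open. The between-groups F is worst with few time points or a gradual effect. The group-by-time F is worst with many time points and low correlation.

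This rests on 128 evaluable patients, d=0.5 on the single-time SD, compound symmetry, and correlations and numbers of time points that I assumed. It is more than a missing detail, because a simple alternative keeps at least 80% power at that N for a full effect at every correlation tried, while both ANOVA terms can fall well below it.

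**What to change.** In section 14, make the deciding test one between-arm comparison, at two-sided .05, of a single HRV value per patient (for example the mean over on-treatment sessions), adjusted for the HRV value taken before the first session. Keep the repeated measures ANOVA as a supportive description of the time course. In any repeated measures analysis, do not read the treatment effect from a between-groups F that counts the pre-treatment value as a response.

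If the sponsor prefers the ANOVA as the deciding test, name the term and replace the stated 0.8 with that term's power at the planned evaluable N, giving the number of time points and the assumed within-patient correlation. In either case, say which SD the effect size of 0.5 refers to.

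**Cost:** a few sentences and one recalculation, with no change to visits or measurements. The time course becomes supportive, and the stated power may look less favourable. The inclusion schedule in section 9 is built on 118 patients. At 59 per arm the unadjusted single comparison has 77% at d=0.5, so the power should be restated for the number actually expected to be evaluable.

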Group 2 (control group) will follow the same intervention protocol as group 1, but without the application of the Andullation® technology. Environmental parameters will be equal to those of group 1.

Producer/distributor

Producer:

International Association of Andullation® Technology (IAAT) - [name] (president dr. [name]) www.iaat.eu

Official dealer:

Home Health Product bvba (HHP) – [name] (CEO [name]) www.hhp.be

Packaging/storage conditions

Normal packaging, transport and storage conditions.

Known side effects

Up to now, there are no negative side effects reported about 20 minutes of Andullation® technology in literature or clinical experience. The Andullation® application is approved as a medical device by TÜV Rheinland Belgium N.V. and FDA massage mattress VM9100RM.

Pregnancy, epilepsy and a recent orthopaedic implant are contra indications reported by the producer and dealer.

Side effects will be registered during the trial.

9) The subjects:

Number of subjects

At the Department of Radiation Therapy of the UZ Brussel, an average of 8 breast cancer patients starts radiation therapy for about 3 to 5 weeks every week. Taking into account the sample size estimation/calculation, the duration of the project (Chair ‘Andullation Care Research’ of the VUB) and the availability of the medical device(s), we have constructed the inclusion schedule below (table 1).

The schedule is based on a 5-week intervention (and control) over a duration of 14 months to include 118 patients for the two study arms. If patients who have only 3 weeks of intervention are included, even more patients can be included. Therefore, insurance is based on the inclusion of maximum 130 patients, taking into account extra (3-week intervention) patients and a drop-out of 10%.

	M1/M2									start/2M	N = (op M14)
	W1	W2	W3	W4	W5	W6	W7	W8	W9		
1st week intervention	2	2	2	2	2	2	2	2	2	18	118
2nd week intervention		2	2	2	2	2	2	2	2		
3rd week intervention			2	2	2	2	2	2	2		
4th week intervention				2	2	2	2	2	2		
5th week intervention					2	2	2	2	2		
interventions/day	2	4	6	8	10	10	10	10	10		
	M13/M14										
	W53	W54	W55	W56	W57	W58	W59	W60	W61		
1st week intervention	2	2	2	2	2						
2nd week intervention	2	2	2	2	2	2					
3rd week intervention	2	2	2	2	2	2	2				
4th week intervention	2	2	2	2	2	2	2	2			
5th week intervention	2	2	2	2	2	2	2	2	2		
interventions/day	10	10	10	10	10	8	6	4	2		

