Table 1: Inclusion schedule of the study.

Inclusion criteria

- Histological proven breast cancer, following breast cancer surgery
- Starting with adjuvant radiation therapy (with or without concomitant chemotherapy) for 3 to 5 weeks
- Age: older than 18 years
- Medical report (possibly for another hospital) is required with:
diagnosis: tumor type and time of 1st biopsy (if relevant)
proposed therapy (start and end dates of each treatment and treatment type)
- Patients have to be able to perform the intervention (laying supine on the mattress for 30', of which 20' intervention)
- A written informed consent has to be signed in the spoken language of the patient. (French, Dutch or English as well as the questionnaires)

Exclusion criteria

- Severe neurological, orthopaedic or rheumatic disorders of the lower or upper limbs which makes it impossible to lay on the mattress in supine position
- Cardiac disorders

- Early or synchronous malignancy
- Pregnancy or lactation
- Persons suffering from depression or illnesses who influence the mental health or wellbeing

Replacement of subjects

A drop-out of 10% was taken into account in the sample size calculation and inclusion schedule. Since we can prolong the intervention with a few weeks (the Chair is assigned for 24 months), we can have an extra medical device of the distributor during the study, we can include more than two patients a week at the UZ Brussel, because there are on average 8 patients starting radiation therapy every week, ... we will be able to anticipate for a bigger drop out.

Restrictions and prohibitions for the subjects

Provocation of vagal nerve activity minimal 24 hours before intervention will be registered prior to every intervention. The use of medication that influences pain sensation, fluid homeostasis, sleep hygiene and stress will be registered.

10) Procedures:

The measurements will be obtained and results will be analysed at the PR4 building of the Universitair Ziekenhuis Brussel, [name].

	Autonomic nervous system	Stress	Pain	Edema	Sleep	Quality of life
Outcome measure	Primary	Secondary	Secondary	Secondary	Secondary	Secondary
Measurement	Heart rate variability through skin sensor (ANSWatch®)			Volume measurement of the arms (Perometer®) for the evaluation of lymphedema Body composition (bioimpedance) for the evaluation of vascular edema		

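### Section 9 says 10% drop-out is in the sample size calculation, but 128 is the uninflated total, and neither 118 nor 130 leaves 128 patients after that loss

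*Combined protocol and SAP*

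**What the plan says.** Section 14 (Study analysis, Sample size calculation) gives the target in one sentence: "with a medium effect size of 0.5 and with a power = 0.8), the total sample size is 128". It does not mention drop-out. The accompanying G*Power output (Figure 5) is not shown in the text available. For the analyses in general, the same section states that "superiority will be based on a two-sided p-value < .05", and it names a repeated measures ANOVA.

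Section 9 (The subjects) gives two further totals.

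- Under Number of subjects, the inclusion schedule is introduced with "Taking into account the sample size estimation/calculation, the duration of the project" and device availability as its basis. It runs "over a duration of 14 months to include 118 patients for the two study arms". The text adds: "If patients who have only 3 weeks of intervention are included, even more patients can be included".
- The same paragraph sets a ceiling: "insurance is based on the inclusion of maximum 130 patients, taking into account extra (3-week intervention) patients and a drop-out of 10" per cent.

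Under Replacement of subjects, section 9 then says: "A drop-out of 10% was taken into account in the sample size calculation and inclusion schedule". It lists ways to recruit more patients and concludes that "we will be able to anticipate for a bigger drop out". It attaches no number to that.

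**The concern.** If 10% loss is already in the calculation, 128 should be larger than the number the test itself requires. It appears to be exactly that number. The schedule said to follow from the calculation is smaller than 128, and the ceiling said to include the 10% exceeds 128 by only 2.

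Two things are at stake. The protocol claims 80% power with 10% drop-out covered, and its own figures may not support that. In addition, three different totals are given, none labelled as enrolled or evaluable, so nobody can say when recruitment is complete or what power the trial was designed to have.

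**Working it through.** **Inputs.** Effect size 0.5, power 0.8 and total 128 come from section 14, as does two-sided 0.05 (stated for the analyses, not in the sample size sentence). The 10% drop-out, the 118 scheduled and the insured maximum of 130 come from section 9. Three assumptions are mine: 0.5 is Cohen's d, allocation is 1:1, and a drop-out contributes nothing to the analysis. Evaluable is my term for those who remain.

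**Step 1: reproduce 128.** For a two-sample t-test, power is the probability that a noncentral t variable with n1 + n2 − 2 degrees of freedom and noncentrality d × √(n1·n2/(n1+n2)) falls outside the two-sided 5% limits.

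- 63 per arm: 0.5 × √31.5 = 2.806, power 79.5%.
- 64 per arm: 0.5 × √32 = 2.828, power 80.1%.

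So 64 per arm, 128 in total, is the smallest equal-arm size that reaches 80%. The match is exact and leaves no room for drop-out.

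**Step 2: look for another route to 128 that includes 10% loss.**

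- One-sided t-test: 51 per arm, 102 in total; 102/0.9 = 113.3, so 114.
- Two-group ANOVA with f = 0.25 (equivalent to d = 0.5): 128, again uninflated. With f = 0.5: about 34.
- Repeated measures ANOVA (f = 0.25 or 0.5; 2 to 15 measurements for the group effect, 2 to 4 for the interaction; correlation 0.3 to 0.7): 6 to 110 in total. The largest, 110/0.9 = 122.2, is still below 128.

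**Step 3: apply the plan's 10% to each stated total** (same t-test, d = 0.5).

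| Patients | Evaluable | Power | d detectable at 80% |
|---|---|---|---|
| 128, no loss | 128 | 80.1% | 0.50 |
| 118, no loss | 118 | 76.8% | 0.520 |
| 130 × 0.9 = 117 | 117 | 76.5% | 0.522 |
| 128 × 0.9 = 115.2 | 115 | 75.7% | 0.527 |
| 118 × 0.9 = 106.2 | 106 | 72.2% | not computed |

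**Step 4: number needed for 128 evaluable.** 128/0.9 = 142.2, so 143 randomised (144 if rounded by arm, 72 each). That is 143 − 130 = 13 above the insured maximum. The schedule falls 128 − 118 = 10 short before any loss.

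**Step 5: where 130 may come from.** 118 × 1.10 = 129.8. This suggests, as an inference only, that the allowance was added to the schedule figure and not to 128.

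**Step 6: the planned analysis.** Power for the repeated measures ANOVA cannot be computed, because the contrast and the correlation between measurements are not given. As an assumed range, take a variance factor of 1 − r² for a baseline-adjusted comparison and 2(1 − r) for a change score. Power with 128 versus 117 evaluable is then:

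| r (assumed) | Baseline-adjusted | Change score |
|---|---|---|
| 0 | 80.1 v 76.5% | 51.0 v 47.5% |
| 0.25 | 82.6 v 79.1% | 63.0 v 59.1% |
| 0.5 | 90.0 v 87.2% | 80.1 v 76.5% |
| 0.7 | 97.6 v 96.4% | 95.2 v 93.3% |

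The shortfall is 1.2 to 3.9 points throughout. The unknown contrast and correlation move power far more than the step from 128 to 117.

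**The case against.** The strongest objection is that Figure 5 is not visible. It may name the test and alpha and may show a drop-out step. This stands as a limit on certainty. A repeated measures group effect with f = 0.25, two measurements and a correlation of 0.8, outside the range tried above, needs 116, and 116/0.9 = 128.9, so 129. A calculation that ends near 128 with loss included is therefore conceivable. It would need a correlation the documents never mention, whereas the plain t-test gives 128 exactly from the stated inputs. Even then, a schedule of 118 would still not match a target of 128.

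Second, counting every drop-out as lost may be too severe. HRV is measured around every session, so a late drop-out would have contributed data. That is fair, but the plan describes no handling of missing data, and a conventional repeated measures ANOVA uses complete cases only.

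Third, recruitment is flexible. Section 9 mentions 3-week patients, an extra device, a longer recruitment period and about 8 new radiotherapy patients a week. The 3-week patients are, however, already counted within the 130. The other measures are offered for a loss above 10%, on the premise that 10% is covered, and no number is given. It is true that 130 is an insurance ceiling and not a declared target.

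Fourth, the effect is small: detectable d moves from 0.50 to about 0.52. That also stands, and it limits how much weight the point should carry.

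**Conclusion.** The concern holds. The statement that 10% drop-out is in the sample size calculation does not agree with 128, which is the uninflated two-sided t-test total for d = 0.5. At the plan's own loss rate no stated total leaves 128 evaluable patients: 130 leaves 117 (76.5% power), 128 leaves 115 (75.7%) and 118 leaves about 106 (72.2%).

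This rests on the inferred t-test, 1:1 allocation, 0.5 read as Cohen's d, and drop-outs contributing nothing. The loss of power is modest, about 3.7 points at 130 enrolled (80.15 − 76.47). The main defect is that 118, 128 and 130 are neither labelled nor reconciled. It should be fixed, but it does not undermine the design.

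**What to change.** In sections 9 and 14:

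1. State in the text the test and alpha behind 128. If Figure 5 confirms the two-sample t-test, label 128 as evaluable patients, 64 per arm.
2. Correct the statement that the calculation includes 10% drop-out, or show the step that includes it.
3. Replace 118, 128 and 130 with one enrolled number and one evaluable number. If 118 and 130 are kept, say what each is (schedule capacity, insurance ceiling).
4. State the power that follows from the evaluable number.

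The choice of number is the sponsor's. On the t-test basis there are two consistent options:

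- **Keep 130 as the maximum.** This gives 117 evaluable, about 76 to 77% power and a detectable d of about 0.52. It needs no extra patients. The cost is wording and a stated power about 3.5 points below 80%.
- **Keep 80% power at 10% loss.** This needs 143 randomised for 128 evaluable (80.1%), so recruitment and insurance must be extended by 13 above the present ceiling.
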